### 3.0 Scientific Endpoints\*

2.1 Describe the scientific endpoint(s), the main result or occurrence under study.

*NOTE: Scientific endpoints are outcomes defined before the study begins to determine whether the objectives of the study have been met and to draw conclusions from the data. Include primary and secondary endpoints. Some example endpoints are: reduction of symptoms, improvement in quality of life, or survival. Your response should **not** be a date.*

Response:

Primary Outcome Measures:

- Clinical Adverse Events assessed at screening, Baseline (BL), and week 24 as well as during a phone call at week 12.
- Blood safety laboratory assessments at screening and week 24 (CBC, CMP, TSH, calcium, ESR, urate, HgA1C and trough serum lithium performed by Kaleida Laboratory Services).
- MRI-based disease-progression biomarkers at BL and week 24:
  - Posterior substantia nigra (pSN), nucleus basalis of Meynert (nbM) and dorsomedial nucleus of the thalamus (DMN-T) free water (FW) levels.
- Blood-based therapeutic targets at BL and week 24:
  - PBMC Nurr1 mRNA levels by real-time polymerase chain reaction (PCR).

Secondary Outcome Measures at BL and week 24:

- PBMC SOD-1 mRNA levels by PCR, PBMC phosphorylated (p) and total (t) levels of pS9 and t-GSK-3 $\beta$ ; pThr308, pS473 and t-Akt (both t and the ratio of p/t will be used for each data point) and plasma interleukin-6 (IL-6) levels by ELISA.
- Trough, steady-state plasma lithium levels assessed by the UB Chemistry Instrument Center utilizing an inductively coupled plasma mass spectrometer (ICPMS) at BL and week 24.
- Clinical Assessments at BL and week 24:
  - Movement Disorder Society-Unified Parkinson's Disease Rating Scale (MDS-UPDRS), Part III (Motor Examination).
  - Parkinson's Anxiety Scale.
  - Geriatric Depression Scale-15.
  - Fatigue Severity Scale.
  - Insomnia Severity Index.
  - Parkinson's Disease Questionnaire-8.
- Montreal Cognitive Assessment (MoCA) at screening and week 24.

## 4.0 Background\*

4.1 *Provide the scientific or scholarly background, rationale, and significance of the research based on the existing literature and how it will contribute to existing knowledge. Describe any gaps in current knowledge. Include relevant preliminary findings or prior research by the investigator.*

Response:

### Background and Preliminary Data:

Parkinson's disease (PD) is the second most common and fastest growing neurodegenerative disorder with a worldwide prevalence that is predicted to more than double over the next 25 years. Although there are several FDA-approved therapies to mask the tremor, stiffness and slowness motor symptoms of PD, no therapies have been shown to slow the progressive worsening of motor symptoms nor the onset of dementia that occurs, on average, within 10 years of diagnosis and represents the most disabling long-term PD sequela. In order to identify therapies that can slow disease progression (both motor and cognitive symptom progression) and improve PD patients' prognosis, a.k.a "disease-modifying therapies", such therapies will first need to show positive effects on therapeutic targets and known disease-progression biomarkers.

A PD therapeutic target of interest for over 25 years is the nuclear receptor-related 1 protein (Nurr1), which is a transcriptional cofactor that upregulates genes essential for dopamine neuron differentiation and survival. Loss of dopamine neurons in the brain's substantia nigra (SN) results in dopamine deficiency and the consequent PD motor symptoms upon which the clinical diagnosis is made. Nurr1 levels decrease in the brain by 46% with aging, which is the main risk factor for PD. In PD patients, Nurr1 message is reduced by an additional 61% in central dopaminergic neurons and peripheral blood mononuclear cells (PBMCs) compared to healthy, aged-matched controls, is inversely correlated with intraneuronal alpha-synuclein levels and ameliorates alpha-synuclein-mediated dopamine cell toxicity. Because alpha-synuclein protein intraneuronal aggregation and inter-neuronal spread is believed to be a principle mediator of the progressive degeneration of neurons in PD, therapies that can increase Nurr1 expression would represent promising disease-modifying therapies. In addition to accumulating and spreading alpha-synuclein, the processes of chronic inflammation and oxidative stress also appear to be critical to the progressive neurodegeneration in PD. Experimental models have shown that when Nurr1 levels are depressed, brain cells become vulnerable to insults and die. One of the genes under the control of Nurr1 is superoxide dismutase-1 (SOD-1), which is a key brain enzyme to reduce oxidative stress. Nurr1 also decreases the expression of alpha-synuclein and reduces inflammation stemming from the brain's principle macrophage, microglia. Thus, increasing Nurr1 expression alone can reduce all three processes critical to progressive neurodegeneration in PD (accumulating alpha-synuclein, chronic inflammation and oxidative stress). Because PBMC gene expression changes have been shown to mirror similar changes in the brain, PBMC Nurr1 and SOD-1 expression represent promising blood-based PD therapeutic targets.

Lithium has multiple neuroprotective actions including suppressing microglial activation, reducing inflammation and oxidative stress, and enhancing autophagy and mitochondrial biogenesis and function. Lithium treatment has demonstrated benefit in several Parkinson's disease (PD) animal models. Also, the 77% risk reduction of PD in smokers shown in prospective cohort studies has been theorized to be due to the high levels of lithium in tobacco. In addition, lithium treatment increases Nurr1 expression by about 180% and protects against rotenone-induced death in PC12 cells. Additional blood-based PD therapeutic targets that lithium may engage include serum brain-derived neurotrophic factor (BDNF), plasma alpha-synuclein and the inhibited form of glycogen synthase kinases-3 $\beta$ , phosphorylated at serine 9 (pS9-GSK3 $\beta$ ), in PBMCs.

Because it is unknown if a therapy's ability to engage blood-based therapeutic targets confers any disease-modifying clinical effects in PD, it is more important to determine a therapy's ability to improve known MRI-based disease-progression biomarkers in PD. Previous analyses of a University of Florida (UF) and the Parkinson's Progression Markers Initiative (PPMI) longitudinal PD biomarker cohorts have shown a diffusion-based MRI assessment called free water (FW) in the posterior substantia nigra (pSN) to longitudinally reflect progressive worsening of motor symptoms. A more recent PPMI analysis showed increasing FW in the dorsomedial nucleus of the thalamus (DMN-T) and nucleus basalis of Meynert (nbM) to reflect progressive worsening of cognition in PD. FW corresponds to water molecules within a voxel that are not hindered or restricted by the cellular environment and therefore originate from extracellular water. There is pathological evidence that FW reflects tissue atrophy and inflammation, which are known to occur in PD. Thus, higher FW levels appear to reflect more advanced tissue degeneration. Thus, a therapy that was shown to slow the longitudinal increases in FW in these brain sites would imply that it was protecting these neurons and, potentially, slowing clinical disease progression. That is, such a therapy would be a highly promising disease-modifying therapy candidate.

Based on the potential disease-modifying effects of the monoamine oxidase inhibitor rasagiline, a recent randomized controlled trial (RCT) assessed rasagiline's effects on pSN FW progression in PD. This RCT showed no significant slowing of pSN FW progression in PD patients randomized to rasagiline compared to placebo for one year. Thus, any preliminary data associating a therapy with slowed or decreasing pSN FW longitudinal changes in PD would be novel and promising.

#### Preliminary Data:

Based on the above background, we conducted an open-label, randomized, pilot trial assessing the effects of three lithium dosages for six months on both blood-based therapeutic targets and MRI-based disease-progression biomarkers among 16 PD patients. This study was funded by the Buffalo Blue Sky Coin program. Because of the limited amount of funding, MRI scans could only be assessed on seven patients. Nevertheless, this pilot study's results showed the lithium aspartate dosage of 45mg/day to robustly engage the therapeutic targets of PBMC Nurr1 and SOD-1 and also to be associated with longitudinal *reductions* in pSN, DMN-T and nbM FW.

In this pilot trial, 16 PD patients were randomized to "low-dose" or "medium-dose" lithium aspartate (15mg or 45mg/day, respectively) or "high-dose" lithium carbonate therapy titrated to a target trough serum lithium level of 0.4-0.5mmol/L for 24-weeks (clinicaltrials.gov: NCT04273932). Three additional PD patients

served as controls and did not receive lithium for 24-weeks. Among the six patients receiving medium-dose lithium, two withdrew due to side effects of sedation and brain fog. No other patients reported side effects. One of the patients who withdrew subsequently resumed lithium aspartate at 30mg/day and reported no side effects with a steady-state trough serum lithium level <0.1mmol/L.

[figure not shown]
Results showed PBMC Nurr1 mRNA levels increased by 420%, 679%, 93% and 139% in the high, medium and low-dose lithium and control groups, respectively, after 24-weeks. Because an *in vitro* study showed that a 180% increase in Nurr1 protected neuronal cells from rotenone-induced death, we defined a “Nurr1 responder” as having a 6-month Nurr1 increase of >200%. With this definition, the Nurr1 responder rates for each lithium dosage and controls were 20%, 75%, 20% and 0%, respectively. Serum lithium levels at six months were 1282, 828, 195 and 0.73µg/L, respectively. In addition, PBMC SOD-1 mRNA increased by 18%, 127%, -1% and 8%, respectively, and by 125% and -21% in Nurr1 responders and non-responders, respectively, after six months. Lithium treatment did not appear to affect PBMC pS9/total glycogen synthase kinase (GSK-3B) ratio levels or plasma alpha-synuclein levels in a dose-response manner.

Thus, the medium-dose lithium group (45mg/day of lithium aspartate) showed the most robust engagement of the PD therapeutic targets Nurr1 and SOD-1 but resulted in severe side effects in 1/3 of the patients. It is unclear why the medium-dose group would show more robust target engagement and more clinical side effects than the high-dose group despite having 35% lower serum lithium levels. We hypothesize that lithium may dissociate from the salt carrier aspartate more readily than from carbonate and/or cross cellular barriers more readily resulting in higher serum and/or intraneuronal “free lithium” levels at equivalent elemental lithium dosages of the two formulations. Because commercial lithium assays typically assess total, not free lithium levels, biological assays like PBMC Nurr1 expression represent a more objective way to compare dose-response relationships among different lithium formulations. This study’s findings of numerically higher magnitudes of PBMC Nurr1 and SOD1 mRNA expression associated with medium-dose lithium aspartate versus high-dose lithium carbonate support this hypothesis. In addition, one of the medium-dose lithium aspartate patients who withdrew due to side effects when receiving 45mg/day subsequently reported no side effects when receiving 30mg/day with a steady-state trough serum lithium level <0.1mmol/L. At 45mg/day of lithium aspartate, the highest predicted serum lithium level in this patient would be about 0.15mmol/L, which would be extremely unlikely to produce side effects if derived from lithium carbonate therapy. In support of this hypothesis, a recent study showed 10-100-fold disparate potencies of several different lithium formulations when assessed on an array of biological assays.

In addition to the blood-based therapeutic target results, the MRI FW results also supported medium-dose lithium aspartate as the most promising dose for further study. Out of the seven patients who received MRI scans at baseline and after 24-weeks of lithium therapy, six had reliable scan data at both timepoints (Figure 1).

Figure 1: Individual Patient Changes in FW after 24-weeks of High, Medium or Low-Dose Lithium Therapy

FW: free water, DMN-T: dorsomedial nucleus of the thalamus, nbM: nucleus basalis of Meynert, pSN: posterior substantia nigra

Table 1 shows the mean longitudinal FW changes in each of these regions of interest (ROIs) in lithium treated PD patients from this pilot study and well as non-lithium treated PD patients and healthy controls (HCs) from the UF and PPMI longitudinal cohorts (some data provided by [name]). It can be seen that the medium-dose lithium treated group was the only group showing mean longitudinal *reductions* in FW in all three ROIs, which is in contrast to the known natural history of FW progression in PD seen in the UF and PPMI cohorts. These findings suggest that medium-dose lithium therapy is associated with improved neuronal integrity and/or reduced inflammation in these important PD ROIs.

**Table 1: Mean FW Longitudinal Changes from Pilot Lithium/PD Trial, UF and PPMI Longitudinal Cohorts**

	Mean Change in DMN-T FW	Mean Change in nbM FW	Mean Change in pSN FW
High-Dose Lithium (24-Week Changes)	-0.0117 (n=2)	-0.0140 (n=2)	0.0198 (n=2)
Medium-Dose Lithium (24-Week Changes)	-0.0098 (n=2)	-0.0416 (n=2)	-0.0307 (n=2)
Low-Dose Lithium (24-Week Changes)	0.0123 (n=2)	-0.0306 (n=2)	0.0787 (n=2)
PD from UF (1-Year Changes)	---	---	0.038  (n=25)
Aged-Matched HCs from UF (1-Year Changes)	---	---	0.001  (n=19)

PD from PPMI (1-Year Changes)	0.0100 ± 0.030  (n=130)	0.0025 ± 0.041  (n=130)	0.0180 ± 0.055  (n=103)
Aged-Matched HCs from PPMI (1-Year Changes)	0.0005 ± 0.024  (n=58)	-0.0085 ± 0.034  (n=58)	0.0070 ± 0.030  (n=49)

FW: free water, PD: Parkinson's disease, UF: University of Florida, PPMI: Parkinson's Progression Markers Initiative, DMN-T: dorsomedial nucleus of the thalamus, nbM: nucleus basalis of Meynert, pSN: posterior substantia nigra, HC: healthy control.

In summary, this pilot study showed medium-dose lithium therapy to have the most robust therapeutic target engagement of PBMC Nurr1 and SOD-1 mRNA expression and the most robust improvements in known MRI disease-progression biomarkers but to also have a high rate of side effects. Also, these results stem from only four and two patients receiving this lithium dosage with blood-based and MRI biomarker data, respectively. If similar results were found in a larger number of PD patients treated with medium-dose lithium therapy in a manner to improve clinical tolerability, such preliminary data would form a strong grant application to the Michael J Fox Foundation and/or the NIH to support a larger RCT.

## 5.0 Study Design\*

*5.1 Describe and explain the study design (e.g. case-control, cross-sectional, ethnographic, experimental, interventional, longitudinal, observational).*

Response:

We will enroll 15 additional PD patients within five months. Eligible patients will have PD for <4 years diagnosed by a movement disorder specialist (Drs. [name] or [name]), be 45-80 years old, have normal thyroid and renal function at the screening visit, have no previous exposure to lithium therapy, have no history of brain surgery, have no hx of brain imaging findings suggesting another neurological condition besides PD, have no use of tobacco or THC products for >1 year, have stable PD medications for >30 days without current need for adjustments in the investigator's opinion, and have stable psychiatric and diuretic medications for >60 days with no anticipated need for changes for at least 24 weeks.

All patients will receive medium-dose lithium aspartate therapy (30-45mg/day) for 24 weeks ensuring that the study will be completed within 12 months. The following dose titration will be used in order to minimize side effects: 10mg bid x 1 week, then 15mg bid x 1 week, then 20mg bid x 2 weeks, then 20mg qAM and 25mg qhs thereafter. Patients will be contacted weekly over the first 4-6 weeks to assess for side effects that are likely to be due to lithium, such as sedation, dizziness or confusion. If side effects occur and are bothersome to the patient, the dose will be decreased incrementally to a minimum of 30mg/day. Such a design will enable identification of the maximum tolerated dose for study in a future trial and maximize the number of patients receiving the most promising dose (45mg/day) identified in the previous pilot clinical trial. Blood-based biomarkers and MRIs will be assessed at baseline and 24 weeks.

The primary blood-based biomarker outcome measure will be change in PBMC Nurr1 mRNA expression from baseline to 24 weeks, which will be compared with the data from the three control PD patients from the pilot study using ANCOVA. PBMC mRNA expression will be assessed by quantitative real-time PCR using TaqMan probes to match the pilot study's methodology. Based on the

22% standard deviation among the three control patients and the 540% treatment effect size for the primary outcome from the pilot study results, only two patients would be needed to detect a difference with 95% power at a 2-tailed alpha of 0.05. Secondary outcome measures will include 24-week changes in PBMC SOD-1 expression, PBMC pS9/total glycogen synthase kinase-3B (GSK-3B) and pThr308, pS473 and t-Akt and plasma interleukin-6 (IL-6) levels. Blood-based biomarkers will be assessed by [name]. Statistical analyses will be performed by [name].

The primary MRI outcomes will be 24-week MRI changes in DMN-T, nbM and pSN FW. Using ANCOVA, these outcomes will be compared with the known natural history of such changes in PD derived from the UF and PPMI longitudinal cohorts summarized in Table 1. In addition, secondary comparisons will be made between changes in these lithium-treated patients and age-matched and disease-duration-matched PD subsets from PPMI.

Exploratory clinical outcomes will include changes in Movement Disorder Society-Unified Parkinson's Disease Rating Scale (MDS-UPDRS) Part III (Motor Examination) with subjects in the "on" state, Montreal Cognitive Assessment (MoCA), Parkinson's Anxiety Scale, Geriatric Depression Scale-15, Fatigue Severity Scale, Insomnia Severity Index and Parkinson's Disease Questionnaire-8. Adverse events and medication compliance will be assessed at a three month phone call. Trough serum lithium and safety labs including HgA1C will be assessed at each visit. Because both baseline and on-treatment lithium levels will mostly be below the level of detection using conventional clinical laboratory services (i.e. Kaleida or Quest), these assays will be performed by the UB Chemistry Instrument Center under the direction of [name]. A protocol was developed by Drs. [name] and [name] for these assays for the pilot study that provided reliable results able to detect baseline lithium levels in all patients prior to initiation of lithium therapy.

The MRI protocol will include a 3D T1-weighted image that will be optimized with the new Philips 3T scanner. Similarly, a multi-shell diffusion weighted imaging acquisition will also be optimized for free water imaging. We will use a sequence with a longer repetition time (6400ms) in order to avoid aliasing T1 effects. In addition, a b=0 image will be acquired with opposite phase encoding to facilitate susceptibility-induced geometric distortions. 3D T1-weighted images will be corrected for intensity inhomogeneity using the N4 tool and subsequently segmented using the SIENAX tool to obtain partial volume estimate maps of the grey matter. The nbM will then segmented as previously described. Briefly, a histologically defined map of the nbM will be brought into the native 3D T1-weighted image space for each scan via non-linearly warping with Advanced Normalization Tools. In addition, each 3D T1-weighted image will be processed using the FreeSurfer 6.0 pipeline along with the thalamic nuclei segmentation submodule. Outputs will be visually inspected for errors and misclassification. Manual corrections to the FreeSurfer output (e.g., introduction of white matter control points, editing of brain mask, white matter mask) will be made as appropriate. For obtaining a mask of the DMN-T, the following individual nuclei will be combined into a single segmentation: paratenial, reuniens (medial ventral), mediodorsal medial magnocellular and mediodorsal lateral parvocellular. pSN regions of interest (ROI) will be obtained using previously published methodology. Briefly, the b=0 image will be aligned to MNI space using an affine registration. Next, the pSN will be drawn using ROIs that include 10 voxels that span two axial slices on each image. The dorsal slice will contain a rectangular

region of interest of six voxels ( $2 \times 3$ ) and the ventral region of interest will consist of a square region of interest of four voxels ( $2 \times 2$ ). The resulting ROIs will then be brought back into native space using the corresponding inverse transformation. Finally, the nBM and DMN-T maps will be brought into the diffusion space using boundary based registration between the 3D T1-weighted image and the  $b=0$ . The maps of the nBM, DMN-T, and pSN in diffusion space will be used to obtain free water values within each ROI.

The diffusion-weighted imaging acquisition will be corrected for susceptibility-induced and eddy current/subject movement-induced distortions using a combination of the FSL tools topup and eddy. Next, the corrected diffusion weighted data will be processed with the free water elimination model implemented in DIPY (<https://dipy.org>) to obtain free water maps. Occipital FW changes will serve as an internal quality control since this ROI is known to have relatively small longitudinal FW changes over 1 year in PD. For example, data from PPMI showed 1-year pSN and occipital FW changes in PD to be 11.6% and 0.25%, respectively. In the lithium/PD pilot study, 24-week occipital FW changes ranged from -8% to 5% among the six patients with valid MRI scans. In the proposed study, patients with occipital FW changes of at least 14% from baseline to Week 24 will be excluded from the MRI outcome analyses as such changes would indicate an MRI acquisition anomaly at either visit.

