**Statistical analyses:**

All statistical analyses of outcomes at each time point will be performed using identical methodologies. The statistical assessment of each considered outcome will be based on a standard analysis of variance (ANOVA) model. In this case, each outcome will be fit as a function of randomized group assignment, baseline cognition, and the interaction between group assignment and baseline cognition. Rather than utilizing the null distribution associated with the classic tests for treatment differences within the ANOVA framework which is dependent on the validity of distributional assumptions, an exact permutation testing approach will be utilized. The randomization mechanism at work is a crucial component in this study in that it will be used to create the randomization distribution by which statistical significance will be determined. Reported p-values will be obtained from the permutation distributions of the test statistics based on 10,000 Monte Carlo simulations. All possible pairwise comparisons will be made between the three treatment groups in conjunction with a Bonferroni adjustment for multiple comparisons performed at a 0.05 family-wise error rate. All statistical tests will be two-sided. In addition, since the comparability of treatment groups may be questioned due to chance imbalance in confounding variables, covariates will be added to the above models as a series of secondary analyses. The interaction of patient covariates and randomized assignment will be examined so to assist in the identification of patient subgroups of interest. All adverse events will be recorded during the study period and then tabulated at the end of the study along with the results of the physical exams. All available data from subjects who fail to complete this study will be included in the safety summaries. The probability of an adverse event will be estimated for each treatment group along with the 95% exact confidence interval based on the method of Clopper and Pearson. All analyses will be carried out using SAS version 9.4 (or higher) statistical software (Cary, NC).

*19.2 If applicable, provide a power analysis.*

*NOTE: This may not apply to certain types of studies, including chart/records reviews, survey studies, or observational studies. This question is asked to elicit*

*whether the investigator has an adequate sample size to achieve the study objectives and justify a conclusion.*

Response: N/A

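### Section 5.1's two-patient figure for 95% power on Nurr1 gives treated patients the SD of three untreated controls; the pilot's medium-dose results imply a treated SD at least 14 times larger

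*Combined protocol and SAP*

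**What the plan says.** Section 5.0 (item 5.1) makes change in PBMC Nurr1 mRNA from baseline to 24 weeks the primary blood-based outcome. It is to be compared by ANCOVA with the three untreated controls of the pilot. The sample-size statement rests on two inputs, the "22% standard deviation among the three control patients" and "the 540% treatment effect size for the primary outcome from the pilot study results", and concludes that "only two patients would be needed to detect a difference with 95% power at a 2-tailed alpha of 0.05". No SD for treated patients is given. The trial enrols 15.

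Section 4.1 (Preliminary Data) supplies the pilot results: "Results showed PBMC Nurr1 mRNA levels increased by 420%, 679%, 93% and 139% in the high, medium and low-dose lithium and control groups". A responder is defined "as having a 6-month Nurr1 increase of >200" per cent, and "the Nurr1 responder rates for each lithium dosage and controls were 20%, 75%, 20% and 0%, respectively", in the order high, medium, low, control. The summary after Table 1 adds that "these results stem from only four and two patients receiving this lithium dosage" with blood-based and MRI data respectively, so the medium-dose Nurr1 result comes from four patients.

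Section 19.2, which asks for a power analysis, is answered N/A.

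**The concern.** A two-group comparison needs the variability of both groups. The calculation takes the SD of untreated patients and uses it for treated patients as well. The pilot responder split shows that medium-dose patients differed widely from one another: one of the four stayed at or below 200% while the group figure was 679%. A spread of 22 points around 679 cannot produce that.

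This is the only sample-size statement in the document. It makes 15 patients look far more than enough and hides the fact that power for the real comparison depends heavily on how the model treats the two variances. Section 4.1 says the results are meant to support an application for a larger randomised trial, so an SD of 22% could be carried forward into that design.

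**Working it through.** **Inputs.** Medium-dose increase 679%, control increase 139%, responder cut-off 200%, medium-dose responders 75% (section 4.1). Four medium-dose patients with blood data (summary after Table 1). Control SD 22, three controls, effect 540, two-sided alpha 0.05, 95% power, 15 new patients (section 5.1).

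**1. Reproduce the plan's figure.** The effect is 679 − 139 = 540. With SD 22 in both groups, the normal formula gives n per group = 2 × [22 × (1.960 + 1.645) / 540]² = 0.043, which rounds up to 1. A t-test with equal groups needs at least two per group. With SD 22 in both groups, simulated power for two against two and for two against three is above 99%, with or without pooled variances. So the figure of two follows from the stated inputs, but only with the control SD in the treated group.

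**2. Smallest treated SD that fits the pilot.** Three of four patients exceeded 200%, so one value x was at or below 200. Let d = 679 − x, so d is at least 479. For a given x, the SD is smallest when the other three values are equal, each d/3 above the mean. The sum of squares is then d² + 3(d/3)² = 4d²/3, and

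SD = √[(4d²/3)/3] = 2d/3.

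- x = 200: the others are (4 × 679 − 200)/3 = 838.7; SD = 2 × 479/3 = 319.3.
- x = 139 (the control mean): SD = 2 × 540/3 = 360.
- x = 0: SD = 2 × 679/3 = 452.7.

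The minimum is 319.3/22 = 14.5 times the SD used. If 22% is a coefficient of variation, the control SD is 0.22 × 139 = 30.6 points and the ratio is 319.3/30.6 = 10.4.

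**3. Power at realistic treated SDs.** Simulation with normal data, a difference of 540, control SD 22, three controls, and two-sample t-tests on raw change without baseline adjustment:

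| Treated SD | 2 v 3 equal var. | 2 v 3 unequal var. | 15 v 3 equal var. | 15 v 3 unequal var. |
|---|---|---|---|---|
| 319 (lower bound) | 65% | 18% | 90% | >99% |
| 400 | 55% | 14% | 63% | >99% |
| 492 | 47% | 12% | 35% | 97–98% |
| 600 | 41% | 10% | 17% | 90% |

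**4. Why the two models part at 15 against three.** At SD 319.3 the true standard error of the difference is √(319.3²/15 + 22²/3) = √(6,798 + 161) = 83.4, and 540/83.4 = 6.5. Pooling gives the variance (14 × 319.3² + 2 × 22²)/16, an SD of 298.8, and a standard error of 298.8 × √(1/15 + 1/3) = 189. Then 540/189 = 2.9, against a critical value of 2.12 on 16 df. Pooling assigns the large treated variance to the three controls and more than doubles the standard error.

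**The case against.** The arithmetic reproduces, and the plan openly names the control SD as its basis, so this is a poor assumption rather than a slip in calculation. That is fair, but it does not rescue the conclusion, because the document's own pilot figures contradict the assumption.

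Section 4.1 does not say that 679% is an arithmetic mean of individual changes. This stands as a caveat. The reading is supported by 679 − 139 matching the stated effect and by responders being defined on individual changes.

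The 319 is a bound on a sample SD from four patients. With 3 df and normal data, an observed SD of 319 is compatible with a population SD of about 181 to 1,191. At 181, two against three still gives about 90% (equal variance) or 31% (unequal variance), short of 95%.

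The study is exploratory, enrols 15 rather than two, and never says that 15 came from this calculation. That limits the consequence, but an incorrect power figure still needs correcting.

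Three stronger readings are tempting and should not be drawn.

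- A reader might infer from "an exact permutation testing approach will be utilized" in section 19.1 that two against three has no power at all, since ten arrangements allow no p-value below 0.10. But 19.1 describes randomised assignment among three treatment groups, which the present single-arm stage lacks, and the power sentence belongs to the ANCOVA in 5.1.
- A reader might take 319 to 492 as a range for the SD. The 492 is itself a minimum, from the high-dose carbonate group with five patients inferred, and no new patient receives that formulation. In the table it is only a sensitivity value.
- A reader might conclude that three controls set a ceiling on power. The low equal-variance figures come from pooling unequal variances; with the same three controls, the unequal-variance test at SD 492 reaches 97–98%.

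**Conclusion.** The point holds. Two treated patients do not give 95% power for Nurr1. At the smallest treated SD that fits the pilot, power is about 65% or 18%, depending on the test. The treated SD is at least 14 times the value used, or about 10 times if 22% is a coefficient of variation.

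The documents do not support the further inference that 15 patients are too few. At the lower-bound SD, 15 against three has about 90% power with pooled variances and over 99% without pooling. What is at risk is the pooled analysis, since a standard ANCOVA pools: its power drops quickly as the SD rises above 319, while the unequal-variance figure stays at about 90% or more up to an SD of 600.

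These results assume that 679% is the mean of individual percent changes, that the full 540-point difference is real, and that data are normal. They are two-sample calculations; the baseline adjustment of the ANCOVA was not modelled.

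**What to change.** Delete the two-patient sentence from section 5.1. In its place, and in section 19.2 instead of N/A, state the power for 15 treated patients against the three pilot controls for a 540-point difference. Give the control SD as 22%, saying whether this means percentage points or a coefficient of variation. Give the treated SD as a lower bound of 319 derived from the pilot, with larger values such as 400 and 600 as sensitivity cases. If the individual pilot values are at hand, the actual medium-dose SD should replace the bound.

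Specify an unequal-variance analysis for the Nurr1 comparison before the data are analysed, for example a baseline-adjusted model with a separate residual variance per group, which the SAS software named in section 19.1 can fit.

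The cost is a text edit and one line in the analysis specification. No patients, visits or assays are added.
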